- (B) The two experimental groups, (groups A and B) will present lower craving scores in relation to the placebo group (group C will receive sham rTMS four sessions per day of intermittent theta burst, for three minutes per session, for five consecutive days, while watching a smoking video as a cue for craving) after the end of rTMS treatment,
- (C) We investigate the difference between the presentation or absence of visual cue among the two experimental groups (group A and B that will both receive real rTMS, with the difference that group B will not be presented a smoking video as cue for craving) as to whether presentation or absence of stimuli influences outcome of craving scores.

Method

Participants

Recruitment of participants will be done through public advertisements of the study, as participants belong in the healthy population. Individuals who agree to participate in this study will be volunteers. The minimum number of participants required was determined by an a priori power analysis where at least a sample size of 100 participants was suggested. (*Measures that suggested this sample size were determined by the mixed model, a small to medium effect size (0.4), at an alpha level of probability of 0.05).

Inclusion criteria of participants will be: (a) to be native speakers of the Greek language, (b) to be over the age of 18, (c) to be tobacco dependent users that wish to quit smoking.

Exclusion criteria of participants will be: (a) individuals with metallic parts inside or near the skull, (b) dependency of any other substances apart from nicotine and caffeine.

For the purposes of this study, participants will be formed into three groups. The groups will be as described below:

(A) An experimental group of 34 participants that satisfy all criteria for inclusion. This group will receive real rTMS, four sessions per day of intermittent theta burst, for three minutes per session, for five consecutive days, while watching a smoking video as a cue for craving;

(B) An experimental group of 34 participants that satisfy all criteria for inclusion. This group will receive real rTMS, four sessions per day of intermittent theta burst, for three minutes per session, for five consecutive days, with no presentation of the smoking video as a cue for craving, but a neutral video;

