(C) A control group of 34 participants that satisfy all criteria for inclusion. This group will receive sham rTMS four sessions per day of intermittent theta burst, for three minutes per session, for five consecutive days, while watching a smoking video as a cue for craving.

Design

This is a randomized, double-blind, sham-controlled study.

Procedure

Prior to the study

After advertisement of the study, potential participants will be able to contact the researcher via contact details that will be given on the advertisement. The researcher will then perform a screening interview (either by phone or email correspondence) regarding the eligibility of participants. The questions will include demographics and contact details: a) telephone number, b) email address, c) sex, d) education and occupation, e) age; and the screening will involve questions regarding eligibility: f) “how many cigarettes do you smoke per day?”, g) “for how long have you been a smoker?”, h) “has there been any period in your life that you managed to quit smoking; if yes for how long and how did you manage to do it?”, i) “are you dependant on any other substances e.g. alcohol/drugs/benzodiazepines apart from caffeine and nicotine”. These questions will be asked in Greek. If individuals meet the criteria and wish to continue, the researcher will arrange with participants details regarding their visit to the site.

At the research site

Participants will arrive at the Cyprus rTMS Centre, will receive all the required information about their participation, and if agreed, they will sign the consent form and will be led to the testing room. Participants will then complete three questionnaires on a PC, prior to the beginning of the experiment. The questionnaires are all described in Materials section and they are attached in the Appendix. All participants will undergo a breath carbon monoxide (CO) measure prior to each TMS session of each day with the use of a smokerlyzer. Further information about its use is described in the section below.

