These questionnaires will be administered to each participant prior to the first day of TMS treatment, after the last day of TMS treatment, after one week, after one month, and after six months. Participants will complete the questionnaires on a 14" laptop at baseline and first follow up, and then online during the remaining follow ups. The aim of the questionnaires will be to test for nicotine dependence, levels of craving, and screening for anxiety levels of participants at different time points. Those data will then be used for within and between participants' analyses. Further, participants will be asked through a visual analogue scale ranked from 1-100 "How much do you want to smoke right now?", prior and after each TMS session, as previously used by Revital Amiaz in similar methodology studies, to assess cue-induced craving of participants.

Smokerlyzer

Smokerlyzer is a non-invasive tool that measures the amount of CO on a smoker's breath and establishes smoking status biochemically. It will be used prior to each TMS session every day for each participant and its measures will be later used for analyses purposes.

Craving Videos

Two videos will be used during the TMS sessions, presented in a randomized manner. The first video is a smoking video which lasts for three minutes and its purpose is to be a cue for inducing craving. The other video used will be a neutral video, illustrating daily tasks that do not involve smoking. This video will be used as a control video.

TMS Protocol

This study will attempt to use accelerated theta burst stimulation of TMS, and specifically the 3-minute FDA-approved protocol for depression. rTMS will be applied to each participant for a period of five consecutive days. Each day will consist of four sessions of the 3-minute theta-burst stimulation with a 45-minute gap (which is the optimal gap) between sessions. The protocol includes 2 seconds of stimulation on the left dorsolateral prefrontal cortex which is followed by an 8 second pause. There will be 600 pulses in total for each 3-minute session. The site of stimulation will be the left DLPFC. It will be measured by using the 10-20 system, it will be determined by the Beam F3 software and it will be at 100% of the motor threshold.

Planned Analysis

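### The protocol means to recruit healthy volunteers, but no stated criterion, listed screening question or on-site step addresses a personal history of seizure or epilepsy

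*Combined protocol and SAP*

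**What the plan says.** **Target population.** Method, Participants: "Recruitment of participants will be done through public advertisements of the study, as participants belong in the healthy population". The health of participants is given as the reason for advertising publicly. It is not defined and is in neither criteria list.

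**Criteria.** The same section lists three inclusions: "to be native speakers of the Greek language, (b) to be over the age of 18, (c) to be tobacco dependent users", the last with a wish to quit. It lists two exclusions: "individuals with metallic parts inside or near the skull, (b) dependency of any other substances apart from nicotine and caffeine".

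**Remote screening.** Procedure, Prior to the study, describes an interview by phone or email. After contact and demographic items, "the screening will involve questions regarding eligibility". Those listed ask about cigarettes per day, years of smoking, past quit periods, and "are you dependant on any other substances e.g. alcohol/drugs/benzodiazepines apart from caffeine and nicotine". The rule for going forward is: "If individuals meet the criteria and wish to continue, the researcher will arrange with participants details regarding their visit to the site".

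**On site.** Procedure, At the research site, describes information, consent, three questionnaires, breath carbon monoxide, head measurement and coil placement. Materials names the questionnaires: nicotine dependence, tobacco craving and perceived stress.

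**Stimulation.** TMS Protocol: "Each day will consist of four sessions of the 3-minute theta-burst stimulation with a 45-minute gap", over five consecutive days. On site and intensity: "it will be determined by the Beam F3 software and it will be at 100% of the motor threshold".

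**The concern.** The stated intent and the rule that carries it out do not match. The sponsor describes a healthy population, but the rule for admission is meeting the criteria, and nothing in the criteria turns on seizure history. A researcher who applied the written rule exactly would admit someone whom the stated intent would presumably keep out.

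What is at stake is participant safety in the two active arms, which receive an accelerated stimulation schedule. There is also a smaller matter of trial conduct. If a seizure history comes to light only after allocation, the protocol gives no rule for it, and removing the person then means a post-randomisation exclusion. Asking beforehand avoids that.

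**Working it through.** There is no figure in the plan to reproduce. The check is a reading of each step at which a volunteer could be stopped, followed by a count of planned exposure.

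**1. Criteria (Participants).** 3 inclusions + 2 exclusions = 5 stated criteria. Their subjects are native language, age, tobacco dependence with a wish to quit, metal in or near the skull, and other substance dependence. Number that address seizure or epilepsy: 0 of 5.

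**2. Remote screening (Prior to the study).** No listed question asks about seizure or epilepsy. The substance question mentions benzodiazepines, but it asks about dependence, not why a medicine was prescribed, so it would not reliably identify epilepsy. The list also has no question on skull metal, native Greek or wish to quit, all of which are stated criteria. It is clearly not exhaustive, so its silence is supporting evidence only. The finding rests on step 1.

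**3. On-site steps (At the research site; Materials).** None of the three questionnaires is a medical history or a stimulation safety screen. The data to be recorded are demographics, questionnaire responses and breath carbon monoxide, with no medical history.

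**4. The intent sentence.** It explains the recruitment route. No criterion, question or procedure applies it.

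**5. A test case.** Take an adult native Greek speaker with epilepsy who is tobacco dependent, wishes to quit, has no metal in or near the skull and depends on no other substance. All three inclusions are met and neither exclusion applies. Under the rule for going forward, the site visit is arranged, and no later step described asks about the condition.

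**6. Planned exposure.** Inputs from Participants and TMS Protocol: 34 per group, three groups, two of them active; 4 sessions a day; 5 days; 600 pulses a session.

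- Total planned: 34 × 3 = 102
- Active: 34 + 34 = 68, and 68 / 102 = 66.7%
- Sessions each: 4 × 5 = 20
- Pulses each: 20 × 600 = 12,000

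One sentence in the Introduction refers to five 3-minute treatments. The group descriptions and TMS Protocol all give four a day for five days, so 20 is the supported count. The 34 participants in group C attend the same number of sessions but receive sham.

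**The case against.** **The risk is not in the documents.** This stands. The Introduction calls rTMS safe and names no group for whom it is unsuitable. It also describes an earlier smoking study at the same intensity, 100% of motor threshold, so the intensity is not in itself a warning sign. That a seizure history matters is a clinical premise and has to be labelled as one. The mismatch between intent and criteria does not depend on it. The sponsor has also written one exclusion about metal near the coil, which suggests it accepts that a participant's characteristics can make stimulation unsuitable.

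**The healthy-population sentence already excludes epilepsy.** This stands only as evidence of intent. Undefined and outside the criteria, the sentence gives the researcher nothing to apply.

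**A safety declaration may exist elsewhere.** This stands as a limit. Consent pages were removed and the Appendix is not shown. The protocol says only that the questionnaires are in the Appendix, and any checklist would have no written criterion on which to exclude someone.

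**Stronger readings.** A reader might infer that people with epilepsy will be stimulated in practice, or that no safety screening takes place. The documents do not show this, because informal screening or an unseen checklist could stop them. A reader might also put a probability on enrolling such a person. The documents give neither a prevalence nor a harm rate, so any such figure would reflect only its assumed input. Finally, a reader might extend the gap to implanted devices away from the head. The coil is over the left DLPFC, skull metal is already excluded, and nothing in the documents suggests a risk to devices elsewhere.

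**Conclusion.** The point holds for seizure and epilepsy: 0 of 5 stated criteria address it, and no listed question or described on-site step makes up for that. As written, a volunteer with epilepsy can be eligible and randomised, with 68 of 102 places (66.7%) leading to 20 active sessions. It should be fixed before recruitment, as a cheap safety improvement that carries out the sponsor's own intent.

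Confidence in the textual finding is high. The consequence rests on the clinical premise that seizure history raises the risk from stimulation, which the clinician responsible for stimulation should confirm. The size of any harm cannot be estimated from the documents. The arms, endpoints and analysis are unaffected.

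**What to change.** 1. In Participants, add exclusion (c): personal history of seizure or epilepsy. If other neurological conditions should exclude, the clinician responsible for stimulation should name each one; a general phrase would be as hard to apply as the word healthy is now. The visible text names only the researcher, so the sponsor should identify who that clinician is. Whether implanted devices elsewhere in the body matter can be left to the same person.

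2. In Prior to the study, add two screening questions: one on seizure or epilepsy, and one on metal in or near the skull.

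3. In At the research site, confirm both answers after consent is signed and before randomisation. The protocol does not say when allocation takes place, so the amendment should state that it follows this check.

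4. If a stimulation safety checklist is already in use, cite it in the protocol and say which answers exclude.

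**Cost.** A short amendment, two questions and a brief confirmation at the first visit. A few volunteers become ineligible and recruitment is slightly slower. The documents give no basis for a more exact number.

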The researcher will then take the appropriate head measures using the 10-20 system and then will place a cap on the participant's head. The participant will sit on the TMS chair and the researcher will place the (real/sham) TMS coil on the participant's left DLPFC and start the session. While participants will be receiving TMS, they will be presented with a smoking video as a cue for craving, throughout each TMS session (except for one group that they will not be presented with a cue craving video, but with a neutral video). There are two available videos, and those will be presented in a randomised manner for each participant. After each session, participants will have a forty-five minute break and then return for the next TMS session. Once done with all five days of TMS therapy, they will be again assessed with the three questionnaires.

To protect personal data and for conditions to be double-blind (participants will not know whether they receive real or sham TMS and researcher will not know whether they administer real or sham TMS), participants will be pseudo-anonymised on an excel database and will be assigned in a randomised manner to each defined group. Demographic and personal data of participants will be confidential only to the researchers involved in the study and will be protected and handled according to the Data Protection Act 2018 and the ICH Good Clinical Practice for data protection. Recorded data of participants will include: demographic details, data of self-report questionnaires at baseline and follow up measures, and CO breath levels.

Following TMS treatment

Following the end of the rTMS treatment, participants will be contacted again to complete the three questionnaires. This will be done at one week, one month and six months post-TMS treatment.

Materials

Questionnaires

The tools used in this study are three questionnaires:

- The Fagerstrom Test of Nicotine Dependence (in Greek),
- The Factor Structure of Tobacco Craving-Short Form (will be adjusted to Greek),
- The Perceived Stress Scale (in Greek).

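### The end-of-treatment craving questionnaire has no set interval or common cue condition after a last session whose video differs by group, so A versus B and B versus C at that visit may mix treatment effect with acute cue reactivity

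*Combined protocol and SAP*

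**What the plan says.** **Baseline.** Procedure, At the research site: "Participants will then complete three questionnaires on a PC, prior to the beginning of the experiment". No video has been shown by then.

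**Sessions.** The same section says of participants receiving TMS that "they will be presented with a smoking video as a cue for craving, throughout each TMS session", except for one group, which sees a neutral video. The group definitions under Participants give the smoking video to A (real rTMS) and C (sham) and the neutral video to B (real rTMS). Under Craving Videos the protocol says of the smoking video that "its purpose is to be a cue for inducing craving".

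**First post-treatment assessment.** At the research site: "Once done with all five days of TMS therapy, they will be again assessed with the three questionnaires". Materials, Questionnaires, gives the schedule as "prior to the first day of TMS treatment, after the last day of TMS treatment, after one week, after one month, and after six months", with completion on a "laptop at baseline and first follow up, and then online during the remaining follow ups". Neither place states hours or days after the last session, a cue-free period, or a cue condition common to the groups.

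**Analysis.** Hypothesis C compares A with B on craving scores and names no time point. Planned Analysis specifies a mixed model over baseline and follow-ups, adjusted for sex, age and visual stimuli.

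**The concern.** The question behind hypothesis C, in the Objectives, is whether provocative cues during stimulation improve the reduction in craving. That is a treatment effect. If the end-of-treatment form is completed shortly after the last video, A and C answer in a recently provoked state and B does not, while all three groups answered unprovoked at baseline. Any acute rise in craving would count against A in A versus B, in favour of B in B versus C, and against A in its own change from baseline (hypothesis A). The visit could not then tell a lasting effect of cue plus stimulation from a momentary reaction to the last video.

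This concerns the questionnaire score and its timing. The 1-100 visual analogue ratings before and after each session are intended to capture cue-induced craving and are a separate measure.

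**Working it through.** The plan gives no figure for acute cue reactivity, so there is none to reproduce. The check has three parts.

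**1. Is a same-day, post-video assessment what the plan describes?**
- For: the sentence stands under At the research site, directly after the description of sessions and breaks. The one-week and later contacts have their own heading, Following TMS treatment. The first follow-up uses the laptop, as baseline does; later ones are online.
- Against: the Questionnaires section says after the last day, not after the last session, and elsewhere uses session-level wording when it means it (the visual analogue rating).
- Result: completion soon after the last session is the natural reading and complies with the plan, but the text does not establish it.

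**2. Can the planned adjustment remove a video effect?** Code an intercept, indicators for B and C, and video (1 = smoking, 0 = neutral):

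| Group | Intercept | B | C | Video |
|---|---|---|---|---|
| A | 1 | 0 | 0 | 1 |
| B | 1 | 1 | 0 | 0 |
| C | 1 | 0 | 1 | 1 |

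Video = 1 − B in every row, so the four columns have rank 3. Video and group cannot both be estimated, and adjusting for visual stimuli cannot isolate an acute cue effect from A versus B.

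**3. How much could it matter?** Inputs: 34 per arm (Participants); alpha 0.05 (Participants), taken as two-sided because sidedness is not stated; an acute shift of b SD in the smoking-video arm, which is an assumption.

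Two-sample t test at the single visit: standard error in SD units = √(1/34 + 1/34) = 0.2425; degrees of freedom = 34 + 34 − 2 = 66; noncentrality = b / 0.2425. For b = 0.2 this is 0.82; for b = 0.5 it is 2.06.

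With no true A-B difference:

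| b (SD) | 0 | 0.1 | 0.2 | 0.3 | 0.4 | 0.5 |
|---|---|---|---|---|---|---|
| Rejection rate | 5.0% | 6.9% | 12.8% | 23.0% | 36.9% | 52.8% |

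For b above zero the rejections lie mostly, and from 0.2 SD almost entirely, in the direction against A. At b = 0.2, 12.56 of the 12.84 percentage points are.

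If A were truly better than B by 0.4 SD (also an assumption; the plan's 0.4 has no stated metric), the chance of showing it would be 36.9% at b = 0, 12.6% at b = 0.2 and 2.5% at b = 0.4.

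For B versus C with no true difference, the chance of a finding in favour of B would be 2.5% at b = 0 and 12.6% at b = 0.2, if C shifts by b.

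If the group contrast were instead averaged equally over the four post-baseline assessments, the shift in it would be b/4, for example 0.2/4 = 0.05 SD. The plan does not say which contrast will be reported.

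**The case against.** The strongest reply is that the timing is inferred. After the last day could mean a later assessment, and with a long enough gap nothing carries over. That stands, and it is why the range must start at zero. It does not remove the point, because the plan allows a site to give out the laptop straight after the last video.

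Second, three of the four post-baseline questionnaires (one week, one month, six months) follow no session and already give an A-B comparison without a same-day video. That stands and limits the problem to one visit. But no main time point is named for hypothesis C, and the end-of-treatment score enters the same model.

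Third, neither the size of the effect nor the instrument's sensitivity is documented. The craving questionnaire's items are not in the supplied text, and by the last session A and C have seen the cue in 4 × 5 = 20 sessions, which may have changed their response. This too stands.

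A reader might go further and infer that:
- **the end-of-treatment A-B result will be biased, or even reversed in sign.** That needs both immediate completion and a shift larger than the true effect, and the documents give neither.
- **A versus C is unaffected because both saw the smoking video.** That holds only if real and sham groups react equally to the cue. The Introduction cites work in which stimulation of this site reduced cue-induced craving, so equal reaction cannot be taken for granted.
- **the video is randomised per participant, so the groups are balanced on it.** Sentences under At the research site and Craving Videos can be read that way, but the group definitions fix the video by arm. The wording needs reconciling and does not rescue the comparison.

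**Conclusion.** The concern holds in a limited, conditional form. The plan leaves open both the interval and the cue condition before the end-of-treatment questionnaires, and its natural reading has the groups answering in different states of provocation. If so, A versus B and B versus C at that visit are confounded with acute cue reactivity, and the analysis as planned cannot undo it.

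The rejection rates in the working illustrate sensitivity and do not estimate bias. They rest on an assumed shift, a two-sided test at one visit, equal SDs and complete data. Baseline adjustment would shrink the standard error but not the shift, so it would not lower them. This is worth correcting because the direction is predictable and the change is small. It does not undermine the later follow-ups.

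**What to change.** In At the research site and in Questionnaires, state that all groups complete the end-of-treatment questionnaires under the same cue-free condition, preferably the day after the last session and by the same mode in every group. State that the end-of-treatment A-B and B-C contrasts are read only from that assessment. Alternatively, name the one-week questionnaire as the main time point for hypothesis C. Reconcile the sentences on random presentation of the videos with the group definitions.

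The 45-minute gap already used between sessions would be a weaker choice: nothing in the documents shows that it clears cue-induced craving.

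Cost: a few sentences, and a next-day form with a slightly higher risk of missing data. If that form is online, its mode differs from the baseline laptop, though equally in all groups. The change does not supply the missing sham-plus-neutral-video arm, so B and C would still differ in both stimulation and video.

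### The video can show the researcher who is on real stimulation: only group B sees the neutral video and B is never sham, so the researcher blind is unsupported for 34 of 102 participants

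*Combined protocol and SAP*

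**What the plan says.** The Design section labels the trial without qualification: "This is a randomized, double-blind, sham-controlled study". Procedure, At the research site, says what the blind covers: "participants will not know whether they receive real or sham TMS and researcher will not know whether they administer real or sham TMS".

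The group definitions are under Method, Participants. Groups A and B are each "An experimental group of 34 participants that satisfy all criteria for inclusion", and group C is "A control group of 34 participants that satisfy all criteria for inclusion". Hypothesis (C) at the end of the Introduction sets out the A versus B contrast: "group A and B that will both receive real rTMS, with the difference that group B will not be presented a smoking video". Group B is treated "with no presentation of the smoking video as a cue for craving, but a neutral video". Of group C the plan says "This group will receive sham rTMS four sessions per day of intermittent theta burst", with the smoking video. The Procedure section confirms that the smoking video accompanies every session, "except for one group that they will not be presented with a cue craving video, but with a neutral video".

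The only steps offered in support of the blind are pseudo-anonymised records and random assignment to group. The same section has the researcher position the coil and begin the session, with the video running during stimulation. It does not say who controls the video or whether the researcher can see the screen. It describes no separate operator, no shielding and no check of blinding.

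**The concern.** Blinding of the coil and of the allocation list protects the real/sham distinction only if nothing else in the session reveals it. Here the video can. No group receives sham with the neutral video, so seeing the neutral video settles the question for anyone who knows the layout. The researcher knows the layout. With four sessions a day for five days (TMS Protocol), there are 4 × 5 = 20 occasions per participant to see which video is playing.

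The hypotheses are about craving scores. The craving questionnaire and the visual analogue scale taken around each session are self-reports. They are open to the way an operator behaves and, where participants know or suspect their treatment, to expectancy. Group B is half of the active side of hypothesis (B) and one of the two arms in hypothesis (C). In hypothesis (C), a difference in knowledge of treatment would travel with the cue difference, and the two could not be separated.

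**Working it through.** **Inputs.** Arm sizes and pairings come from Method, Participants: 3 × 34 = 102, consistent with the stated minimum of 100. The argument does not depend on the power calculation.

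| Group | n | Stimulation | Video |
|---|---|---|---|
| A | 34 | real | smoking |
| B | 34 | real | neutral |
| C | 34 | sham | smoking |

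**Step 1: what the video tells an observer who knows this table.**
- P(real), video unseen = (34 + 34)/102 = 68/102 = 67%.
- P(real given neutral) = 34/34 = 100%.
- P(real given smoking) = 34/(34 + 34) = 34/68 = 50%.
- Share identified as real: 34/102 = 33% of all participants, and 34/68 = 50% of those on active stimulation.

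**Step 2: which contrasts are exposed.** A and C see the same video, so A versus C is not exposed. B versus C compares an arm identifiable as real with one at 50:50, and also differs in video content. A versus B compares an arm identifiable as real with one at 50:50.

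**Step 3: can the analysis repair it?** Planned Analysis lists visual stimuli among the adjustment terms. The indicator for the neutral video equals the indicator for group B. In a model with the three-level group factor it is therefore aliased with group and can remove nothing.

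**Step 4: would a pooled blinding check find it?** Without the video, the best strategy is always to guess real, which is right in 68/102 = 67%. With the video, all 34 neutral guesses are right and half of the 68 smoking guesses are right: (34 + 34)/102 = 67%. The pooled rate is the same, so only a check by arm can show the problem.

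**Step 5: illustration of size.** The documents give no expectancy or operator effect. Assume a shift of b SD in group B only, no true effect, and a two-sided 5% z-test. The rejection rate is Φ(d/SE − 1.96) + Φ(−d/SE − 1.96), with SE = √(1/n₁ + 1/n₂) in SD units.
- A versus B, or B versus C: d = b, SE = √(1/34 + 1/34) = 0.243.
- A and B pooled versus C: d = b/2, because only half of the pooled arm is shifted; SE = √(1/68 + 1/34) = 0.210.

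| Assumed b (SD) | A vs B, or B vs C | A+B vs C | A vs C |
|---|---|---|---|
| 0.1 | 7.0% | 5.7% | 5.0% |
| 0.2 | 13.1% | 7.6% | 5.0% |
| 0.3 | 23.6% | 11.0% | 5.0% |

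The plan does not say whether hypothesis (B) is tested by pooling A and B or by separate contrasts, so both are shown.

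**The case against.** A reader might infer that the blind fails outright for a third of participants and that the results of hypotheses (B) and (C) are biased. The documents do not support that.

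- **Participants.** A group B participant sees one video and has no stated reason to link it to real stimulation. The consent pages are not in the available text, so it cannot be checked whether the pairing is disclosed.
- **Operator.** The plan does not say that the operator sees the screen. The questionnaires are completed by participants on a laptop and later online, so no rater scores them. An operator effect would have to act through behaviour, a weaker route than a participant's own expectation. Breath CO is objective and enters the analysis, though it is described only before treatment sessions and the hypotheses concern craving.
- **Size.** It is also tempting to set a 0.1-0.3 SD shift against the plan's effect size of 0.4 and call it 25-75% of the target effect. That needs 0.4 to be an SD difference, and the plan does not state the metric. If 0.4 is Cohen's f with A and B equal and different from C, the difference is 0.4/(√2/3) = 0.85 SD, and the same shift is about 12-35%. The shift itself is assumed in either case.
- **Video assignment.** Procedure and Craving Videos both describe presentation of the videos as randomised. If the video varied within participants, it would not mark an arm. That reading contradicts the group definitions; the reading that fits them is that the video follows the randomised group.

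These points limit the claim to what a researcher could see and a participant might learn. They do not supply the missing masking, and the statement about the researcher remains unsupported for group B.

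**Conclusion.** The concern holds in a conditional form. As designed, the neutral video marks 34 of 102 participants as certainly on real stimulation to any researcher who knows the groups and sees the video, and nothing in the plan prevents that. The double-blind statement is therefore unsupported for group B on the researcher's side. On the participant's side it is open to doubt only if the pairing is disclosed.

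The consequence is exposure to bias, not demonstrated bias, in B versus C and A versus B. A versus C, the sham comparison with the same video, is untouched by this route. The rejection rates of about 7-24% (A versus B or B versus C) and 6-11% (A and B pooled versus C) are illustrations. They rest on an assumed 0.1-0.3 SD shift confined to B and no true effect; neither the size nor the direction of any real shift can be read from the documents.

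**What to change.** 1. Give the two videos coded file names tied to the randomisation code. Play them on a screen out of the operator's view, with sound through headphones. Hiding the pairing itself from researchers who hold the protocol is not workable, so it is the video that must be hidden from them.
2. Do not tell participants which video is paired with sham.
3. At the end of day 5, record the participant's and the operator's guess of real or sham, and report both by arm. Guesses can also reflect perceived benefit, so they should be read with that in mind.
4. Name A versus C as the video-matched, masked test of stimulation. Claim double-blinding for contrasts involving B only if items 1 and 2 were in place and the guesses by arm support it; otherwise report the exposure as a limitation.
5. Reconcile the wording on randomised presentation of the videos (At the research site; Craving Videos) with assignment of the video by group.

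The cost is a small set-up effort, one added question for participant and operator, protocol wording, and possibly a narrower blinding claim. No extra participants are needed. Items 1 and 2 must be in place before sessions run, because masking cannot be restored in the analysis. If sessions are already complete, the narrower claim and the stated limitation remain available.

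A fourth group, sham with the neutral video, would remove the marker altogether: with equal cells, P(real) is 50% under either video. It would need 4 × 34 = 136 participants, or 25-26 per cell at 102, and is not required for the changes above.
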